12.2.1 Laboratory tests

Summary statistics will be presented.

The assessment time points are as follows:

- Double-blind period: Week -2, baseline, Weeks 1, 2, 4, and 6, and at the end of the double-blind period
- Entire study period: Week -2, baseline, Weeks 1, 2, 4, 6, 7, 8, 10, 12, 18, 26, 34, 46, and 58, and at the end of the extension period

12.2.2 Shift table of laboratory data

The numbers and percentages of subjects with values (low, normal, or high) before and after treatment will be presented.

The assessment time points are as follows:

- Double-blind period: Baseline and at the end the double-blind period
- Entire study period: Baseline and at the end of the extension period

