### 8.2.5 Rationale for the doses and the duration of treatment

In a Japanese phase II clinical study (Study MR13A9-4), intravenous administration of MR13A9 0.25, 0.5, and 1.0 µg/kg or placebo 3 times weekly for 8 weeks resulted in significant improvement of pruritus in 0.5 and 1.0 µg/kg groups compared with the placebo group. In addition, there was a dose-response relationship showing a constant effect of MR13A9 at doses of 0.5 µg/kg and higher. As for safety, MR13A9 at up to 1.0 µg/kg was tolerated, but adverse events occurred frequently in the 1.0 µg/kg group. The phase II study in the United State (Study CLIN2101) and phase III study (Study CLIN3102) also confirmed the superiority of the MR13A9 0.5 µg/kg group to the placebo group. Based on the above, it was considered appropriate to select 0.5 µg/kg of MR13A9 as the recommended clinical dose.

In Study MR13A9-4, the effect of MR13A9 to improve itching was constant after Week 4, and all adverse drug reactions occurred before Week 6. Accordingly, 4-week and 6-week periods in the double-blind period were established to allow the efficacy and safety evaluations of MR13A9, respectively. In addition, a 52-week extension period was established to assess the safety of long-term treatment with MR13A9 with reference to the "Extent of Population Exposure to Assess Clinical Safety for Drugs Intended for Long-Term Treatment of Non-Life-Threatening Conditions" (ELD Notification No. 592 dated May 24, 1995).

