5.7.1 Handling of data in tabulation at each time point (excluding symptom diary

data)

- Data will be summarized by time point according to the time windows shown in [Table 5.7.1-1](#). Data obtained outside the time windows will be excluded from tabulation at each time point.
- If multiple data are available within the time window, the data obtained at scheduled visit will be employed.
- Data for observations and tests performed at unscheduled visits or 10 days after the day of the final dose will be excluded from the tabulation.
- For dependency assessment, all data collected will be employed regardless of the time window.

Table 5.7.1-1 Time windows for assessment time points

Assessment time point	Scheduled date ^{a)}	Time window
At Week -2	-14	Scheduled date \pm 3 days
At baseline	1	Day -3 to Day 1
At Weeks 1 to 12	$7 \times x + 1^b)$	Scheduled date \pm 3 days
At Weeks 18 to 58	$7 \times x + 1^b)$	Scheduled date \pm 7 days

a) The start of study treatment in the double-blind period is defined as Day 1 and the day before the start of study treatment as Day -1.

b) x: Number of weeks

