5.7.2 Handling of data in tabulation at the final assessment point

- In the double-blind period, efficacy data (Skindex-16, 5-D itch scale, and PGIC) obtained at Weeks 1 to 4 (or at the time of withdrawal during the double-blind period before Week 4) and safety data obtained at Weeks 1 to 6 (or at the time of withdrawal during the double-blind period) will be included in the tabulation. Data for observations and tests performed at the latest time point within 10 days after the day of the final dose during the double-blind period will be used as the data at the end of the double-blind period. Data for observations and tests performed at unscheduled visits will be excluded from the tabulation.
- For the entire study period, data from Weeks 1 to 58 (or at the time of withdrawal during the extension period) will be included in the tabulation. Data for observations and tests performed at the latest time point within 10 days after the day of the final dose during the extension period will be used as the data at the end of the extension period. Data for observations and tests performed at unscheduled visits will be excluded from the tabulation.

6. Statistical/Analytical Issues**6.1 Adjustments for Covariates**

The change from baseline in the mean NRS score at Week 4 of the double-blind period, the primary variable, will be analyzed using the baseline mean NRS score and the presence of prior treatment with nalfurafine hydrochloride, a dynamic allocation factor, as a covariate. For details, refer to "[11.1.1 Primary variable](#)." If an imbalance is observed in the subject demographics of the FAS, the primary analysis set for efficacy, a supplementary analysis will be performed with

additional items showing the imbalance as the covariates in the primary analysis.

For the changes from baseline in the itch score based on the Shiratori's severity criteria, changes from baseline in Skindex-16, and changes from baseline in 5-D Itch Scale, an analysis will be performed using the baseline as a covariate for each item. Details are shown in "[11.2.1.1 Change from baseline in the mean itch score](#)," "[11.2.2.1 Changes from baseline in Skindex-16](#)," and "[11.2.3.1 Changes from baseline in 5-D itch scale](#)," respectively.

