12.2.3 Scatterplots of laboratory data

Scatterplots of measurements before and after treatment will be presented.

The assessment time points are as follows:

- Double-blind period: Baseline and at the end the double-blind period
- Entire study period: Baseline and at the end of the extension period

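### The laboratory shift tables use only the last on-treatment value, so an abnormality that has returned to range by then is counted in no planned low/normal/high table

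*SAP*

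**What the plan says.** SAP 12.2.2 describes the shift table as follows: "The numbers and percentages of subjects with values (low, normal, or high) before and after treatment will be presented". It gives two pairs of time points: "Double-blind period: Baseline and at the end the double-blind period" and "Entire study period: Baseline and at the end of the extension period". SAP 12.2.3 uses the same pairs for the plots: "Scatterplots of measurements before and after treatment will be presented". SAP 12.3.2 does so for vital signs and body weight.

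SAP 5.7.2 defines the end-of-period value. For the double-blind period it is the observation "performed at the latest time point within 10 days after the day of the final dose during the double-blind period", and for the entire study period the one "performed at the latest time point within 10 days after the day of the final dose during the extension period". Withdrawal tests are eligible and unscheduled tests are not. SAP 5.7.1 has a similar rule for the by-visit tables: "Data for observations and tests performed at unscheduled visits or 10 days after the day of the final dose will be excluded".

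Protocol 14.6.3 asks only for shift tables before and after treatment. Neither document plans a shift to the worst value, to any on-treatment value, or visit by visit.

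On timing, Protocol 8.2.5 reports that in the 8-week Japanese phase II study "all adverse drug reactions occurred before Week 6".

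**The concern.** Laboratory tests are a declared safety endpoint (Protocol 4.2.1), and endocrinology was added because opioids could affect it (Protocol 4.2.2). Protocol 1.3.2.2 lists decreased TSH and increased prolactin among the common drug reactions of the 2-week phase II study, and decreased TSH again in the 8-week study. These lists cover any MR13A9 dose group, not 0.5 µg/kg alone.

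If reactions begin early, Weeks 1, 2 and 4 are where onset would be seen. For a subject with a Week 6 value, none of those visits enters the double-blind shift table. A subject whose TSH falls below range at Week 2 and has recovered by Week 6 appears as normal to normal, the same as a subject who was never abnormal.

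The entire-study table has the same gap for placebo subjects who switch. Their first MR13A9 dose is at Week 6, and visits follow at Weeks 7, 8, 10 and 12. A completer is represented only by Week 58, about 52 weeks after first exposure.

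At stake is the description of laboratory safety, including the randomised comparison. The primary test and the sample size are not involved.

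**Working it through.** **Inputs**
- Post-baseline laboratory visits (SAP 12.2.1): Weeks 1, 2, 4, 6 in the double-blind period, which is 4. Over the entire study: Weeks 1, 2, 4, 6, 7, 8, 10, 12, 18, 26, 34, 46, 58, which is 13.
- Values used per subject in the shift table: 1 per period (SAP 12.2.2 with 5.7.2).
- Group size N = 86 (Protocol 8.6.1). This figure reproduces: a two-sample t-test with difference 1.0, SD 2.0, two-sided 5% and 90% power needs 85.03, rounded up to 86; power at 86 is 90.3%.
- Share of subjects ever abnormal on treatment, p, and share of those back in range by the last value, r. The documents give neither, so both are assumptions shown as a range.

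The plan states no figure on this point that could be reproduced.

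**Step 1: visits that feed the table.** Double-blind: 1 of 4 = 25%. Entire study: 1 of 13 = 8%. These are shares of visits, not shares of abnormalities detected.

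**Step 2: what the last-value table would show.** Treat all 86 as in range at baseline. Expected subjects ever abnormal = N × p. Expected subjects shown as abnormal = N × p × (1 − r).

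| p (assumed) | Ever abnormal | Shown, r = 0 | Shown, r = 0.5 | Shown, r = 1 |
|---|---|---|---|---|
| 3% | 86 × 0.03 = 2.6 | 2.6 | 1.3 | 0 |
| 10% | 86 × 0.10 = 8.6 | 8.6 | 4.3 | 0 |
| 20% | 86 × 0.20 = 17.2 | 17.2 | 8.6 | 0 |

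The loss runs from none to all and depends wholly on r.

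**Step 3: do the documents fix r?** No. Protocol 8.2.5 dates the onset of reactions. Neither document says whether TSH or prolactin returned to range on continued dosing.

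**Step 4: do other displays supply the count?**
- *Per-visit summary statistics* (SAP 12.2.1 with section 4) give mean, SD, minimum, maximum, median and quartiles by group. They do not count subjects out of range or tie a value to that subject's baseline.
- *Adverse events* (Protocol 10.13.1.3, item 3) capture a laboratory change at any visit, but only if the investigator judges it clinically significant. These are then counted by subject and preferred term (SAP 12.1.3).
- *By-subject lists of abnormal values* (SAP 12.6) give no rates. SAP 6.3.1 leaves them out of the double-blind analysis, which SAP 6.5.1 makes the primary one. They fall within the later interim tabulations (SAP 6.3.2).

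None of these counts subjects leaving the normal range independently of investigator judgement.

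**Step 5: the price of a worst-value table.** Assume a stable subject has a 2.5% chance of crossing a given limit at each visit and that visits are independent. The chance of at least one crossing is 1 − 0.975^k:
- k = 4: 9.6%
- k = 9 (Week 7 onward, 13 − 4): 20.4%
- k = 13: 28%

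Correlation between visits lowers these figures. They apply to each limit of each of the 42 analytes in SAP 12.2.

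**The case against.** The strongest defence is that the plan already follows early laboratory changes. The phase II signals were themselves reported as adverse drug reactions, and that route remains open here. A clinically significant change at any visit becomes an adverse event, is counted by group and preferred term over the whole double-blind period, and is tabulated by time of onset for the entire study. Per-visit minimum, maximum and quartiles would show a marked early shift between groups. The lists are deferred, not dropped. The SAP is consistent with Protocol 14.6.3, and a worst-value table adds chance crossings, with no concurrent placebo arm in the open-label extension.

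Most of this stands, and it makes the gap a modest one. It does not supply a count of range crossings that is free of investigator judgement.

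A reader might also infer more than the documents support:
- *That early abnormalities are counted as normal.* Only those back in range are. One still present at the last value is counted as low or high.
- *That the Week 58 table looks where no effect is expected.* Early onset does not imply early resolution. A change that began before Week 6 can persist.
- *That the table misses 3 of 4 (75%) or 12 of 13 (92%) of abnormalities.* Those figures require each abnormality to occupy exactly one visit, equally likely to be any visit. Nothing in the documents supports that, and it conflicts with reactions beginning early.
- *That no other table counts subjects who become abnormal.* The adverse event tables count those judged clinically significant.

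**Conclusion.** The point holds in limited form. The shift tables and scatterplots use baseline and the last eligible value only, and no planned low/normal/high table counts an on-treatment abnormality that has resolved by then. A last-value table therefore cannot separate subjects who were never abnormal from those who were abnormal and recovered. Early laboratory-type reactions are documented for this drug, so the distinction is relevant here.

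The number of subjects affected cannot be stated. At an assumed 10% ever abnormal in a group of 86, the table would show 8.6 subjects if none resolve, 4.3 if half do and 0 if all do. The conclusion rests on the visit schedule and the definition in SAP 5.7.2, not on any assumed rate. It is a cheap improvement to the safety description and not an error that threatens the trial's conclusions.

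**What to change.** In SAP 12.2.2, keep the end-of-period shift table and add a second one:
- Show the shift from baseline to the lowest value and, separately, to the highest value over all scheduled and withdrawal visits within 10 days of the final dose.
- Present it by group for the double-blind period and for the entire study period.
- For the P-MR group in the entire-study table, take the worst value from Week 7 onward, so that placebo visits are not mixed with MR13A9 visits.
- Show results that include unscheduled tests only as a supplement, because closely monitored subjects have more chances to be found abnormal.
- State that the double-blind table is to be read against placebo and the open-label table descriptively, because worst values over several visits raise chance range crossings.

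Changing the scatterplots in SAP 12.2.3 and 12.3.2 is optional.

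The cost is a short SAP amendment and two derived values per analyte and period. No new data are needed, and the primary test and sample size do not change.

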12.2.3 Scatterplots of laboratory data

Scatterplots of measurements before and after treatment will be presented.

The assessment time points are as follows:

- Double-blind period: Baseline and at the end the double-blind period
- Entire study period: Baseline and at the end of the extension period

12.3 Vital Signs and Body Weight

Analysis items are shown below.

- Vital signs: Systolic blood pressure, diastolic blood pressure, pulse rate, and body temperature
- Body weight (before dialysis)

12.3.1 Vital signs and body weight

Summary statistics will be presented.

The assessment time points are as follows:

- Vital signs
 - Double-blind period: Week -2, baseline, Weeks 1, 2, 4, and 6, and at the end of the double-blind period
 - Entire study period: Week -2, baseline, Weeks 1, 2, 4, 6, 7, 8, 10, 12, 18, 26, 34, 46, and 58, and at the end of the extension period

- Body weight
 - Double-blind period: Week -2, baseline, Week 6, and at the end of the double-blind period
 - Entire study period: Week -2, baseline, Weeks 6, 12, 34, and 58, and at the end of the extension period

12.3.2 Scatter plots of vital signs and body weight

Scatterplots of measurements before and after treatment will be presented. The assessment time points are as follows:

- Double-blind period: Baseline and at the end the double-blind period
- Entire study period: Baseline and at the end of the extension period

12.4 Dependency Assessment

12.4.1 Evaluation of dependency based on judgment by dependency assessment members

The number and percentage of subjects will be presented for dependency (negative, positive, not evaluable) and severity (mild, moderate, severe) at the interim and final assessments. However, only subjects with dependency will be included in the tabulation of severity.

12.5 Safety Subgroups

The same analyses as described in “[12.1.1 Incidence of adverse events and adverse drug reactions](#)“ will be performed for each of the subgroups defined by sex (male, female), age (< 65 years, ≥ 65 years), prior treatment with nalfurafine hydrochloride (no, yes), and specific signs or symptoms occurring during the screening period (no, yes).

12.6 Tabulated Lists of Safety Variables

For subjects who entered the double-blind period, lists of death, serious adverse events other than death, adverse events leading to interruption, adverse events leading to discontinuation, adverse events of special interest, and abnormal laboratory values by subject will be prepared. However, the lists will not be prepared if there is no applicable event.

13. Software Used for Analysis

SAS System Release 9.4 for Windows (SAS Institute Inc.) will be used to conduct the analysis. Other statistical analysis software will also be used as needed.

14. Tables, Figures and Listing Shells

The TFL shells will be provided separately.

15. Changes from the Clinical Study Protocol

- 1) Changes in the statistical analysis plan version 1.0

Not applicable.

2) Changes in the statistical analysis plan version 2.0

- (1) It has been decided to conduct 2 interim tabulations.
Reason: To clarify the contents and timing of analysis.
- (2) In “9.1 Subject Demographics,” the mean NRS score (ordinal scale variable) has been added to the analysis items.
Reason: To perform a more detailed evaluation of the distribution of the mean NRS score at baseline.
- (3) In “10.5 Change in Dry Weight Category,” the status of change from the last time of determination of study drug dose has been added, and the text has been modified to clarify the content of the analysis.
Reason: To perform a more detailed evaluation of the status of change in dry weight category.
- (4) In “11.1.2.1 Change from baseline in the mean NRS score,” “11.2.2.1 Changes from baseline in Skindex-16,” and “11.2.3.1 Changes from baseline in 5-D itch scale,” the text has been revised to add graphical presentations for the double-blind period.
Reason: To perform a more detailed visual assessment of the efficacy endpoints in the double-blind period.
- (5) In “11.1.2.3 Percentage of subjects with improvement in the mean NRS score,” the assessment time points in the figure for the entire study period have been limited to some of the time points.
Reason: To perform visual assessment at the limited time points.
- (6) In “11.1.2.4 Change from baseline in the daily NRS score,” “11.1.2.5 Daily NRS score,” “11.2.1.3 Change from baseline in daily itch score,” and “11.2.1.4 Daily itch score,” the assessment time periods have been extended up to Day 15.
Reason: To perform a more detailed evaluation of the efficacy in the early stage of treatment.
- (7) In “11.1.2.4 Change from baseline in the daily NRS score” and “11.2.1.3 Change from baseline in daily itch score,” the text has been updated to include MMRM analysis as performed in the primary analysis.
Reason: To perform an analysis that takes into account the influence of covariates and correlations between time points.
- (8) In “11.2.3 5-D Itch Scale,” component scores (duration, degree, direction, disability, and distribution scores) have been added to the analysis items.
Reason: To perform a more detailed evaluation of the 5-D Itch Scale data.
- (9) In “11.2.2.1 Changes from baseline in Skindex-16” and “11.2.3.1 Changes from baseline in 5-D itch scale,” the variables to be displayed for analysis of covariance have been described.
Reason: To clarify the variables to be displayed.
- (10) In “11.3 Efficacy Subgroups,” the same analysis as described in “11.1.2 Other assessment variables” has been added.
Reason: To perform a more detailed evaluation of the NRS score in subgroups.
- (11) In “11.3 Efficacy Subgroups,” a subgroup defined by the mean NRS score at baseline

(< 6 , ≥ 6) has been added.

Reason: To evaluate whether efficacy varies depending on the mean baseline NRS score.

(12) In “12.1.6 Details of adverse events of special interest,” “adverse events of special interest occurring between the start of study treatment and the end of the extension period” has been added to the events to be tabulated in the entire study period.

Reason: To perform a more detailed evaluation of adverse events of special interest.

(13) In “12.4.1 Evaluation of dependency based on judgment by dependency assessment members,” the description of the target assessments (interim and final) has been added.

Reason: To clarify the target assessments.

3) Changes in the statistical analysis plan version 3.0

(1) “11.2.1.5 Percentage of subjects with improvement in night-time mean itch score” has been added.

Reason: To evaluate in more detail of the improvement in night-time itching.

16. History of Revision of Statistical Analysis Plan

Version	Date of creation/revision	Author	Description
1.0	January 7, 2021	[name]	First version prepared
2.0	November 16, 2021	[name]	Revised version prepared
3.0	October 24, 2022	[name]	Revised version prepared

17. Literature References

- 1) Higaki Y. Skindex-16 (Japanese version): A skin disease-specific quality of life scale. Tokyo. Medical Professional Relations Inc. 2002.
